Assignment to Study Group: Participating children and their primary caregivers will be assigned to one of three groups. Participants will be stratified by age (18-35 months; >36 months) and developmental quotient (DQ<55; DQ ≥55) at project enrollment, prior to being randomized. After stratification, participants will be randomly assigned to the one of the three groups using random permuted blocks of 6. This approach has been shown to yield groups that are closely balanced with regard to size and relevant pre-treatment characteristics. All pre-treatment assessments will be collected prior to randomization to prevent bias during testing based on knowledge of future group placement.

b. Sources of Materials

The sources of data for this study will include: (1) direct assessment of child functioning using standardized assessments; (2) completion of standardized questionnaires by parents; (3) written survey completion by parents; and (4) videotaped coding of treatment processes. All data will be used exclusively for research purposes. All surveys and interviews will use codes rather than subject names. Only the PI and primary research team members will have access to subject identities. Procedures to minimize risk of loss of confidentiality are presented below.

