Parent Measures: Parents will complete the Parenting Sense of Competence Scale at pre-treatment, post-treatment, and follow-up to assess parent self-efficacy. Using the videotapes of the parent-child interaction in the home at pre-, post-treatment, and follow-up, the research team will assess parent use of the intervention strategies. Parents will also be asked to provide demographic information and complete the Parent Expectancies for Therapy Scale, a measure of treatment expectancy, the Computer-Email-Web Fluency Scale, a measure of computer/internet fluency, at pre-treatment, and the Parenting Stress Index, a measure of parenting stress at pre-treatment. Parents will be asked to complete the Treatment Evaluation Inventory, measure of treatment acceptability, at the conclusion of treatment. Parents will complete the Additional Services Form to monitor the type and number of hours per week of all non-study treatments once per month throughout study participation.

c. Potential Risks

There are no known serious health or psychological risks related to participation in this study. Procedures to minimize risk of loss of confidentiality are presented in the following section. In addition, there are legal limits to the confidentiality of information obtained during the research study. All information obtained from participants will be held confidential unless there is serious threat of harm to a child or to self or others. These limitations will be addressed in the consent forms. Collection of data from participants will include standardized child assessment measures, standard parent questionnaires regarding their child's development and behavior, standard parent questionnaires about their well-being and satisfaction with treatment, and videotape recordings. Precautions will be applied to all collected data from these activities, which will be stored in a private, secure and confidential location at MSU. All participants will be made aware of how collected data will be handled.

Adequacy of Protection Against Risks

a. Recruitment and Informed Consent

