Overall Approach. The current study will use the Intention-to-Treat model (ITT) in the analysis of the primary aims. The ITT approach requires that all participants who are randomly assigned be compared on outcomes regardless of their adherence to treatment, reasons for withdrawal, or missing responses. Accordingly, we will include all participants in data analysis, follow up participants who withdraw from treatment, and impute missing data, as described below.

Missing Data. We will use the Expectation Maximization (EM) algorithm in SPSS to impute missing data for analyses that require complete data (e.g., Process Macro).

Preliminary analyses. To determine the comparability of groups on non-treatment variables after randomization, group differences will be examined for all T1 pre-treatment and descriptive variables. If significant group differences are detected for a given variable, and the variable of interest, then the variable will be used as a covariate in subsequent analyses as appropriate.

We will also examine age and DQ effects and identify whether treatment effects are moderated by either.

Aim 1: To examine the comparative efficacy of self-directed and therapist-assisted *ImPACT Online* on parent outcomes at post-treatment and the 3-month follow-up. To test our primary hypotheses for Aim 1, we will use multilevel modeling with restricted maximum likelihood estimation to examine the effect of group assignment on our primary and secondary parent outcomes. Time point (pre-treatment, post-treatment, follow-up) will be coded as a categorical variable. Change over time across groups will be estimated with the main effect of time, and between-group differences in change in outcomes will be estimated with the group by time interaction.

Aim 2: To examine the comparative efficacy of self-directed and therapist-assisted *ImPACT Online* on child outcomes at the 3-month follow-up. Three measures of verbal language will be collected at pre-treatment and follow-up. If child language measures are sufficiently correlated with each other ($r > .50$), we will create an equally weighted composite variable by z-scoring and summing the language measures. ANCOVA will be used to test for mean differences between the three conditions at follow-up. Pretest values will be included as covariates.

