Aim 3: To examine whether pre-treatment parenting stress moderates the effects of *ImPACT Online* on parent fidelity and parent self-efficacy at post-treatment. Pre-treatment parenting stress will be included in the MLM models as a covariate. The pre-treatment parenting stress by time interaction will be used to determine whether pre-treatment parenting stress moderates change over time, irrespective of treatment group. The three-way interaction of pre-treatment parenting stress, group, and time will be used to examine whether the relationship between group assignment and change over time (i.e., group slopes) varied by pre-treatment parenting stress. A significant interaction will be followed up by simple slopes analyses.

Aim 4: To examine whether gains in parent fidelity (or parent self-efficacy) and child intentional communication at post-treatment mediate the effects of the *ImPACT Online* on child verbal language at the 3-month follow-up. We will conduct two serial mediation analyses using the PROCESS macro in SPSS to examine whether gains in parent fidelity (Mediator 1) and child intentional communication (Mediator 2) at post-treatment mediate the effect of *ImPACT Online* in child outcomes at follow-up. A second serial mediation analysis will be conducted to examine whether gains in parent self-efficacy (Mediator 1) and child intentional communication (Mediator 2) at post-treatment mediate the effect of *ImPACT Online* in child outcomes at follow-up.

Aim 5 (exploratory): To identify predictors of parent adherence to *ImPACT Online* for the two treatment groups. This exploratory aim will be addressed using a multiple regression approach in which level of therapist support (self-directed versus therapist assisted) and three individual-level factors (computer and internet fluency, expectancies of treatment, and treatment acceptability) serve as primary predictors of parent adherence. We will also examine sociodemographic variables as predictors as well.

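### One EM-filled file with no pooling is analysed as if fully observed: the Aim 4 mediations by name, Aim 2 by inference, and Aim 5 only on a weak reading

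*Combined protocol and SAP*

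**What the plan says.** Under Overall Approach, the SAP adopts intention to treat for the primary aims and commits that "we will include all participants in data analysis, follow up participants who withdraw from treatment, and impute missing data, as described below". The Missing Data paragraph then gives the only method: "We will use the Expectation Maximization (EM) algorithm in SPSS to impute missing data for analyses that require complete data (e.g., Process Macro". It does not mention a number of imputations, a pooling rule, a variance correction, the variables in the EM model or a missing-data sensitivity analysis.

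The analyses that could be touched are:
- **Aim 4:** "We will conduct two serial mediation analyses using the PROCESS macro in SPSS". PROCESS is used nowhere else, so the rule covers Aim 4 by name.
- **Aim 2:** "ANCOVA will be used to test for mean differences between the three conditions at follow-up", with pretest as covariate. ANCOVA needs complete records, but the rule does not name it.
- **Aim 5:** "This exploratory aim will be addressed using a multiple regression approach". It is also not named. One predictor, treatment acceptability, is measured late: "Parents will be asked to complete the Treatment Evaluation Inventory, measure of treatment acceptability, at the conclusion of treatment".
- **Aims 1 and 3:** multilevel models, which use incomplete outcome records without filling. In Aim 3, "Pre-treatment parenting stress will be included in the MLM models as a covariate", and a missing covariate is not recovered that way.

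The only statement on expected loss is in the design section, which allows for some attrition without giving a rate.

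**The concern.** An EM fill replaces each missing value by a prediction from the observed data. If the completed file then goes to PROCESS or ANCOVA, the software counts predictions as data. The sample size is too large, the filled cases add little or no residual scatter, and the standard errors ignore that the values were estimated. Bootstrapping the completed file does not help, because the imputation is not repeated in each resample.

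The choice of EM variables matters too, and the plan does not state it. For the Aim 2 group test, including group understates uncertainty, while omitting group pulls the filled values of all three arms together and shrinks the effect. For Aim 4, intervals under-cover either way when a true effect exists, and omitting group adds shrinkage.

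At stake are the child-language comparison at follow-up (Aim 2) and the mechanism claims (Aim 4).

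**Working it through.** **Inputs.** N = 90 in three groups, blocks of 6 (30 per group assumed). Pre-to-follow-up correlation .65 for child language and f = .25 (Power Analysis). Assumptions: nominal α .05; 5/10/20/30% missing completely at random; EM fill taken as the conditional mean; percentile bootstrap for Aim 4; path sizes and loss patterns as stated.

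**The plan's own figure.** The plan gives no figure for missing data. Its nearest figure is about 90% power for child language with complete data. By its stated method, effective N = (90 − 3)/(1 − .65²) = 87/.5775 = 150.6 and λ = .25² × 150.6 = 9.42, which gives power .78 for the three-group F test. The stated figure does not reproduce. That is a separate matter and neither supports nor weakens this point.

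**Aim 4, coverage of a true indirect effect (nominal .95).** Half of those missing follow-up also miss post-treatment; M2-to-outcome path .3:

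| Missing | 5% | 10% | 20% | 30% |
|---|---|---|---|---|
| EM, group in | .923 | .927 | .921 | .886 |
| EM, group out | .922 | .925 | .912 | .871 |
| Full-information likelihood | .929 | .936 | .944 | .936 |

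With nothing missing, coverage is .945. Over other loss patterns and path sizes the EM range is roughly .89–.93 at 10% and .82–.90 at 30%. In the run tabled above, omitting group also shrinks the indirect effect to 96/94/90/84% of truth.

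**Aim 4, false positives with EM, group in.**

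| Data lost | Null path | 10% | 20% | 30% |
|---|---|---|---|---|
| Follow-up only | last | .088 | .117 | .181 |
| All post-baseline | group to M1 | .089 | .142 | .188 |
| Follow-up, half also post-treatment | last | .053 | .068 | .102 |
| All post-baseline | last | .043 | .045 | .043 |

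Complete-case rates are .056/.038/.042 for the first row and .059/.069/.064 for the second. The last row shows no inflation because a filled family sits at its group's fitted point on every variable and adds nothing to the within-group slope.

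**Aim 2, whole follow-up visit lost, group in EM.** The filled estimate is close to the available-case one. Let d be the missing fraction and v = 90(1 − d) − 4 the true residual df. The software uses 86 df and the full N, so the reported F is about k times the valid F, with k = (86/v)/(1 − d). The critical value F(2, 86) is 3.103, so the actual type I error is P(F(2, v) > 3.103/k) = (1 + 2x/v)^(−v/2), where x = 3.103/k.

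| d | v | k | x | Type I, formula | Type I, simulated |
|---|---|---|---|---|---|
| .05 | 81.5 | 1.111 | 2.793 | .067 | .070 |
| .10 | 77 | 1.241 | 2.500 | .089 | .090 |
| .20 | 68 | 1.581 | 1.963 | .148 | .153 |
| .30 | 59 | 2.082 | 1.490 | .234 | .238 |

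Available-case ANCOVA gives .053/.050/.049/.048 and pooled multiple imputation .046/.052/.047/.048. Adding one random residual to each fill does not cure the problem: .080/.127/.192 at 10/20/30%.

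This is the upper scenario. If one of three measures in a composite is missing, the rates are .059/.056/.057/.069. With a post-treatment auxiliary variable of assumed partial r .5, they are .063/.077/.120/.178.

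**Aim 2, group out of EM.** A fraction d of each arm carries no group difference, so the expected effect is (1 − d) of truth: 95/90/80/70% (simulated 95/89/80/70%). The estimate's variance is (1 − d)² × σ²/[n(1 − d)] = (1 − d)σ²/n, which equals the reported variance, so type I error holds at .053/.049/.049/.048. Coverage of a true effect falls to .943/.931/.885/.788.

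**Aim 5, acceptability missing, two groups of 30.** With adherence in the EM model, type I error for acceptability is about .06/.08/.13/.18. With adherence out, it is .051/.054/.051/.048, and a true coefficient of .30 is estimated as .299/.302/.299/.300.

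**Power, Aim 2, f = .25, 20% missing.** EM shows .84, but at a type I error of .153. Held to a true 5% level it has .66, against .67 for available-case ANCOVA.

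**The case against.** The strongest reply is that the harm needs missing data, and losses may be small. Families who withdraw are to be followed up, assessments are scheduled in the home, and each is paid. Assessments mix direct testing, interview and on-line forms, so partial loss, the milder case, is plausible. That stands as a limit on size. It does not make the method sound, and the plan itself expects attrition.

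A reader might infer more than the documents support:
- **That the primary parent result is compromised.** It is not. Aim 1 uses a REML multilevel model, which handles missing outcomes by likelihood. Aim 3 is touched only if a stress score is missing, which should be rare because "All pre-treatment assessments will be collected prior to randomization".
- **That Aim 5 will produce false predictors.** The intention-to-treat sentence covers only the primary aims, and Aim 5 is exploratory. Only the general words about analyses needing complete data reach it, and the harm disappears if adherence is left out of EM.
- **That mediation false positives are always inflated, or always near nominal at low loss.** Neither holds; the table shows both outcomes.
- **That Aim 2 type I error will be inflated.** This needs Aim 2 to be in scope and group to be in EM, and it is marked only when whole visits, or most measures, are lost.
- **That only multiple imputation will do.** Available-case ANCOVA holds its level equally well under these assumptions.

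That there is one completed file is itself inferred from silence on repetition and pooling. It is the plain reading.

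**Conclusion.** The concern holds in graded form and should be fixed. Confidence is high for Aim 4, moderate for Aim 2 and low for Aim 5. The plan does more than leave out detail: it names a method that understates uncertainty or, depending on the unstated EM variables, shrinks effects.

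The most general result is Aim 4 under-coverage when an indirect effect exists; it appears in every loss pattern examined, with group in or out, although with group out part of it is shrinkage. Aim 4 false positives must be read as a range: no inflation at one end, and about .07–.09 at 10% and .13–.19 at 30% missing at the other. The Aim 2 figures are larger but conditional. All sizes assume loss completely at random at rates the plan does not state.

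**What to change.** Replace the EM sentence in the Missing Data paragraph.
- **Aim 4:** use a full-information maximum likelihood path model, or repeat the imputation within each bootstrap resample.
- **Aim 2:** use a likelihood-based model or available-case ANCOVA. Alternatively, use multiple imputation that includes group, stratification factors, pretests and post-treatment measures, pooled by Rubin's rules. If imputation is chosen, keep available-case ANCOVA as a sensitivity analysis.
- **Aim 5:** if it is imputed at all, use pooled multiple imputation with adherence and its predictors in the model.
- **Scope:** name the aims the rule covers, list the imputation variables, and say how a missing stress score is handled in Aim 3.

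The number of imputations and the bootstrap scheme can be left to the trial statistician.

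The cost is SAP wording and modest analysis work. Aim 4 may have to be run outside PROCESS or looped over resamples, and intervals will be wider. The apparent loss of power is only the removal of excess type I error.

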Child Measures: Child diagnostic testing will be conducted at pre-treatment. We will also examine specific child characteristics (cognitive ability level, language level, autism severity) that are predicted to be related to the impact of the parent-implemented interventions. We will administer the Autism Diagnostic Observation Scale, 2nd Edition (ADOS-2) to the child at pre-treatment. The ADOS-2 is a standardized protocol for observation of social and communicative behavior associated with a diagnosis of ASD that has been shown to have high reliability and discriminant validity. Recent longitudinal studies have demonstrated that diagnostic stability for children under age 3 is best when using DSM-IV based clinical judgment in conjunction with results from standardized diagnostic instruments, such as the ADOS. As in previous studies, this is the approach that will be used in the present study in order to determine a specific DSM-V diagnosis for each child. The PI has established research reliability on the ADOS. She will train the clinical research staff on these methods (as needed) and supervise all assessments. Child cognitive ability will be assessed using the Mullen Scales of Early Learning at T1. Child intentional communication with the parent will be scored from a parent-child interaction in the home at pre-treatment and post-treatment using weighted frequency of intentional communication. Language outcomes will be assessed at pre-treatment and follow-up using the

Mullen Scales of Early Learning, a parent report measure (the MacArthur-Bates Communicative Development Inventory) and the Vineland Adaptive Behavior Scales.

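### The Aim 2 ANCOVA leaves out the age and DQ factors used to stratify randomisation, and the baseline-significance rule will almost never bring them in

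*Combined protocol and SAP*

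**What the plan says.** **Design.** Under Assignment to Study Group, "Participants will be stratified by age" (18-35 months against over 36) and by DQ (below 55 against 55 or more). Then, "After stratification, participants will be randomly assigned to the one of the three groups using random permuted blocks of 6". The plan expects this to work: "This approach has been shown to yield groups that are closely balanced with regard to size and relevant pre-treatment characteristics".

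**Aim 2 model.** The Statistical Analysis Plan compares the three arms at follow-up by ANCOVA and names one kind of covariate: "Pretest values will be included as covariates". The Power Analysis section likewise treats the pre-test score as the covariate.

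**Other covariates.** Preliminary analyses tests the arms against each other on all baseline and descriptive variables and continues: "If significant group differences are detected for a given variable, and the variable of interest, then the variable will be used as a covariate", to be applied where appropriate.

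**Age and DQ elsewhere.** The same section adds: "We will also examine age and DQ effects and identify whether treatment effects are moderated by either". It gives no model for this and does not connect it to the Aim 2 comparison.

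**The concern.** The plan treats age and DQ as important enough to balance by design, then specifies an analysis that ignores them. The only stated way in is a significant difference between arms, which stratification is there to prevent. The rule is therefore least likely to pick these two factors, however prognostic they are. The phrase about the variable of interest is unclear. It may also require a relation to the outcome, but on either reading a significant baseline difference is needed.

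Two things are at stake.

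- **Efficiency.** Stratification removes the factors' variation from the comparison of arm means, while a pretest-only model leaves it in the error term. If the factors predict follow-up language beyond pretest, the standard error is too large. The test then rejects too rarely under the null, and power already paid for in the design is lost.
- **Pre-specification.** The Aim 2 covariate set is not fixed until baseline data have been tested, so two analysts following the text could fit different models.

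**Working it through.** **Inputs from the documents:** N = 90; three arms; permuted blocks of 6 within 4 strata; language pretest-to-follow-up correlation r = .65; f = .25.

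**Assumed, because not stated:** alpha .05; equal allocation; equally spaced arm means; complete data; and p, the share of the variance left after pretest that the strata explain, shown from 0 to 30%.

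**1. The plan's own figure.** The Power Analysis gives about 90% for this test. Its method (divide by 1 − r², one extra participant per group) gives an ANOVA-equivalent N of 3 × (30 − 1)/(1 − .65²) = 87/.5775 = 150.6. The noncentrality is 150.6 × .25² = 9.42 and power is 78.1%. The same method gives 80.9% for fidelity (stated 80%) and 89.0% for self-efficacy (stated 90%). The language shortfall is a separate matter. It is noted here only because the figures below start from 78-79%, not 90%.

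**2. Analytic power.**
- Pretest only: noncentrality = 90 × .25²/(1 − .65²) = 5.625/.5775 = 9.74. Error df = 90 − 3 − 1 = 86. Power .790.
- Pretest plus two binary factors: noncentrality = 9.74/(1 − p), error df = 84.

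| p | Noncentrality | Power with strata |
|---|---|---|
| 0 | 9.74 | .789 |
| .05 | 10.25 | .811 |
| .10 | 10.82 | .833 |
| .20 | 12.18 | .876 |
| .30 | 13.91 | .917 |

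**3. Simulation of the stratified design.** There were 8,000 replicates per cell. The follow-up score was .65 × pretest + √(1 − .65²) × (√p × S + √(1 − p) × e) + arm effect. S is the standardised sum of the two factors after removing pretest, and e is noise. Four set-ups ran from no overlap with pretest to pretest coefficients of .3 (age) and .5 (DQ), with factor prevalences of 50/50 or 30/40. Ranges are over set-ups.

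| p | Power, pretest only | Power, with strata | Type I error, pretest only |
|---|---|---|---|
| 0 | 78-79% | 78-79% | .048-.051 |
| .05 | 78-80% | 80-81% | .044-.048 |
| .10 | 78-79% | 82-83% | .034-.044 |
| .20 | 79-80% | 87-88% | .023-.034 |
| .30 | 79-80% | 91-92% | .015-.024 |

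Type I error with strata was .048-.055 throughout. Within set-ups, the gain was 1.6-2.2 points at 5%, 3.5-3.9 at 10%, 7-8 at 20% and 11-12 at 30%. The lowest type I errors need no overlap with pretest. A separate simulation with 70% of children in the older stratum and a latent DQ-pretest correlation of .5 agreed: 78.3% against 80.1% at 5%, and 78.5% against 82.5% at 10%. With 77 children analysed, the 10% case was 72.0% against 76.0%.

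**4. Which shares are plausible.** Child Measures says "Child cognitive ability will be assessed using the Mullen Scales of Early Learning at T1", and lists the language measures as "Mullen Scales of Early Learning, a parent report measure (the MacArthur-Bates Communicative Development Inventory) and the Vineland Adaptive Behavior Scales". The source of DQ is not stated but is probably the Mullen, so DQ and pretest language probably overlap. If the DQ factor correlates q with pretest, a share p from DQ alone requires a DQ-to-follow-up correlation of .65q + √p × √((1 − .65²)(1 − q²)).

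| q | p = .05 | .10 | .20 | .30 |
|---|---|---|---|---|
| .5 | .47 | .53 | .62 | .69 |
| .3 | .36 | .42 | .52 | .59 |

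The larger shares make strong demands; 30% is an upper bound.

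**5. How often the rule selects age or DQ.**
- Binary factors (chi-square, p < .05): 0 of 20,000 trials.
- Continuous age (one-way F), 10,000 trials under each of two assumed age distributions: 42 and 12 trials, or 0.4% and 0.1%.
- Continuous DQ, same trials: 9 and 4, under 0.1%.
- Very uneven strata (90/10 and 80/20): either continuous variable selected in 2.5% of trials.

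**The case against.** The strongest reply is that nothing here threatens a conclusion. The comparison is unbiased, type I error is not inflated, and at a 5% share it is close to nominal. The loss depends on an association that the documents do not give.

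It may also be small. The correlations in step 4 are for a binary DQ split. Under normality and a median split (attenuation about .80), .47 and .53 at q = .5 correspond to about .59 and .67 for continuous DQ, so a 10% share would need DQ to predict follow-up slightly better than pretest does at .65. If continuous DQ correlates .6 with pretest and .45 to .60 with follow-up, DQ alone gains only 0.2 to 2.7 points. From a 90% base, shares of 5% and 10% add about 1.5 and 2.9 points. The composite's pre-post correlation is unknown, so r = .65 may not apply to it.

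On the text, the rule says when a variable is added, not that nothing else may be. The plan also promises to look at age and DQ effects, and moderation models would normally carry their main effects.

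The argument about size stands: 4 points is not a central estimate, and the 20-30% rows only mark the outer range. The textual reply does not close the gap. No other route into the Aim 2 model is given, and a promise to examine age and DQ does not say which model is primary. The question is that choice of model, not neglect of the factors.

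**Conclusion.** The concern holds. As written, the main Aim 2 test omits both stratification factors, and the significance rule would almost never restore them. If they explain 5% of the variance left after pretest, about 2 points of power are lost; at 10%, about 4. At 0% nothing is lost, and including them costs about 0.1 point (.790 against .789). The low end is more plausible. The error is on the conservative side: intervals too wide and tests too cautious, with no added false positives.

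The size rests on an assumed share, alpha .05, equal allocation, complete data and the plan's r and f. The omission, and the covariate set left open until baseline data are tested, do not depend on those assumptions. This is a modest point worth correcting because the correction is nearly free.

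**What to change.** In the Aim 2 ANCOVA, pre-specify three fixed covariates: the pretest value, and the age and DQ factors in the binary form recorded at randomisation. Delete the significance-based covariate rule and report baseline comparability descriptively. Keep any model adjusted for an observed imbalance as a sensitivity analysis, and keep the planned age and DQ moderation analyses as secondary.

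No change to the Aim 1 model is asked for beyond deleting the rule. Only strata that predict change in parent outcomes would matter there, and the documents suggest no such link.

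The cost is a few sentences in the Statistical Analysis Plan and two error degrees of freedom (86 to 84). No new data are needed.

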Protocol for Comparative Efficacy of Self-directed & Therapist-assisted Telehealth Parent
Training Intervention for Children With ASD

NCT02721381

Based on last approval by MSU IRB on 4/6/2020

Risk to Human Subjects

a. Human Subjects Involvement, Characteristics, and Design

A total sample of 90 children with ASD between the ages 18-96 months and their primary caregivers will be recruited for this study. This sample size was determined to be adequate for maintaining adequate power for the proposed statistical analyses, while allowing for some attrition.

Inclusion Criteria for Families: To be eligible for participation, 1) the child must receive a DSM-V-informed clinical diagnosis of Autism Spectrum Disorder, based on the *Autism Diagnostic Observation Schedule* (ADOS). The diagnosis may be provisional for children under age 3 (typically listed as "at risk for ASD"). Children with this classification will be included as well. (2) The child must fall between the ages of 18 - 96 months at enrollment into the study, which will allow for data collection during the period of early intervention and early childhood special education programming. (3) The parent must understand spoken English as the training materials are presented in English.

Exclusion Criteria for Families: (1) Children with ASD who have a history of significant brain injury or known neurological condition in addition to a diagnosis of ASD, significant sensory impairment or major medical problems. These children and their families may require very specific adaptations to the treatment and thus the results will not be representative of children with ASD. This will be determined through review of medical records, diagnostic reports and parent interview. Criteria and data sources for identifying participants are outlined below.

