Power Analysis. A series of power analyses were conducted using Borm, Fransen, & Lemmens⁸⁹ method for estimating sample size for analyses including a covariate. This approach takes into account the degree of association between the covariate and the outcome (r) by adjusting the required sample size required for an analysis without a covariate by $1 - r^2$ and then adding one extra participant per group. In our case, the covariate is the outcome variable as assessed at the pre-test. Analyses predicting parent fidelity (i.e., Aims 1 & 2) assumed a T1 to T2 correlation in fidelity of $r = .35$, and for self-efficacy, the T1 to T2 correlation was assumed to be $r = .75$. Across the aims involving parent fidelity we found that a sample size of 90 participants would provide 80% power to detect moderate to large effects of treatment condition (e.g., Cohen's $f = .32$). For parent self-efficacy a sample of 90 would provide 90%

power to detect moderately sized treatment effects (e.g., $f = .25$). For the child language variables we assumed a correlation between pretest and follow-up of approximately $r = .65$ for each of the three measures. Analyses predicting child language variables at follow-up controlling for pretest language scores (i.e., Aims 2 & 4) indicated that a sample size of 90 participants will have approximately 90% power to detect a moderate effect size ($f = .25$) for treatment condition.

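### The 80% power for parent fidelity assumes pretest adjustment, but Aim 1 plans a group-by-time test with pre-treatment as a level of time, so the figure does not describe the planned test

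*Combined protocol and SAP*

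**What the plan says.** Under Aim 1, the SAP plans a multilevel model fitted by REML for the parent outcomes. On the time factor it says: "Time point (pre-treatment, post-treatment, follow-up) will be coded as a categorical variable". On the treatment effect it says: "between-group differences in change in outcomes will be estimated with the group by time interaction". It does not say whether group means are free or equal at pre-treatment, gives no covariance structure, and does not say which contrast carries the inference.

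Under Aim 2 (child language), the planned analysis is ANCOVA, and there the SAP does say "Pretest values will be included as covariates". Aim 1 has no such sentence.

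The Power Analysis section uses a sample-size method for analyses with a covariate: take the N needed without a covariate, multiply by 1 − r², and add one participant per group. It states "In our case, the covariate is the outcome variable as assessed at the pre-test". For fidelity it assumes r = .35 between pre- and post-treatment and an effect of f = .32, and concludes: "Across the aims involving parent fidelity we found that a sample size of 90 participants would provide 80% power".

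**The concern.** Having the pretest in the outcome vector is not the same as adjusting for it. If each group has its own mean at every time point and data are complete, the pre-to-post part of the group-by-time interaction is the difference between groups in mean change. Change scores carry the full noise of the pretest, whereas a pretest covariate removes only what the pretest predicts. With a correlation as low as .35 the two error variances can differ a good deal.

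Aim 1 holds the plan's primary hypotheses, and this power figure is part of the case for 90 participants. If the planned test is the less precise one, the trial has less chance of detecting the stated fidelity effect than the SAP claims. The Preliminary analyses rule, which adds a covariate when groups differ significantly at T1, is conditional and does not supply planned pretest adjustment.

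**Working it through.** **Inputs from the documents.** N = 90 in three groups; fidelity r = .35 and f = .32; self-efficacy r = .75 and f = .25.

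**Assumptions not in the documents.** Alpha .05; 30 per group; complete data; f expressed on the post-treatment SD; k = pretest SD / post-treatment SD. All power values come from the noncentral F distribution with noncentrality λ.

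**1. The plan's own figure.** Without a covariate, f = .32 needs N = 98 for 80% power. The plan's adjustment gives 98 × (1 − .35²) + 3 = 98 × .8775 + 3 = 89, in line with N = 90. The exact ANCOVA at N = 90 has λ = 90 × .32² / .8775 = 10.50 on F(2, 86), and power 82.1%. The stated 80% is therefore sound for a pretest-adjusted analysis.

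**2. The planned post-treatment contrast, group means free at pre-treatment.** In units of the post-treatment variance, a change score has variance 1 + k² − 2rk = 1 + k² − .70k. Then λ = 90 × .32² / (1 + k² − .70k) on F(2, 87).

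| k | Variance | λ | Power at N = 90 | N for 80% (equal groups) |
|---|---|---|---|---|
| .5 | .90 | 10.24 | 81% | 90 |
| .8 | 1.08 | 8.53 | 73% | 105 |
| 1.0 | 1.30 | 7.09 | 65% | 126 |
| 1.2 | 1.60 | 5.76 | 55% | 156 |
| Pretest-adjusted, any k | .8775 | 10.50 | 82% | 87 |

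The two variances are equal only at k = r = .35. Power of the planned contrast drops below 80% at k of about .57. At k = 1 it is below that of a post-treatment comparison that ignores the pretest (λ = 90 × .32² = 9.22, power 76.6%), because r is under .5. Simulation at k = 1 (20,000 runs for each of two patterns of means) gave 64.3% to 64.4% for the change contrast and 81.6% for ANCOVA.

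**3. The 4-df interaction over three waves.** Here λ = 90 × .32² × d′V⁻¹d, where d holds the relative effects at post-treatment and follow-up. V is the covariance of the two changes from pre-treatment for the planned test, on F(4, 174). For the adjusted test it is the covariance of the two later waves given the pretest, on F(4, 172). With k = 1, equal SDs at the later waves and a pre/follow-up correlation of .35 (assumed):

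| Effect at follow-up | Post/follow-up r | Planned | Adjusted |
|---|---|---|---|
| Fully kept | .35 | 67% | 92% |
| Fully kept | .68 | 60% | 82% |
| Half kept | .35 | 53% | 76% |
| Half kept | .68 | 60% | 74% |
| Gone | .35 | 67% | 76% |
| Gone | .68 | 91% | 93% |

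For the first row, λ is 9.45 planned and 16.68 adjusted. The adjusted test is ahead in all six rows. At k = .5 the same six gaps shrink to between 0 and 2 points.

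**4. Self-efficacy at k = 1.** The change variance is 2(1 − .75) = .50, giving λ = 90 × .25² / .50 = 11.25 and power 85%. The adjusted variance is 1 − .75² = .4375, giving λ = 12.86 and power 89%.

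**The case against.** The strongest reply is that the text is under-specified and not plainly wrong. Aim 1 names a time main effect and a group-by-time term but no group main effect, and that is also how a model with one common pre-treatment mean would be written. The 65% is a single scenario: it needs k = 1, free pre-treatment means and a 2-df post-treatment contrast that the SAP never names. At k = .5 the shortfall all but disappears. The adjusted 4-df test itself ranges from 74% to 93%, so 80% would not describe that test either. Finally, the Power Analysis section assigns fidelity to Aims 1 and 2 although Aim 2 now concerns child language, so the power text may simply be older than the aims.

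Much of this stands as a limit on the size of the loss: it depends on k, and the documents give no SDs to settle it. It does not remove the mismatch. Nothing in Aim 1 states a common pre-treatment mean, and most analysts would fit the full factorial from this description. Aim 2 shows that the authors state pretest adjustment where they intend it. If the power text is out of date, it still needs correcting.

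**Conclusion.** The concern holds. The 80% for parent fidelity is correct for a pretest-adjusted analysis and does not describe the Aim 1 test as conventionally read. The mismatch itself is certain; the size of the loss is conditional. With alpha .05, 90 complete cases, free pre-treatment means and f on the post-treatment SD, the post-treatment contrast has between 81% (k = .5) and 55% (k = 1.2) power, and 65% with equal SDs, against 82% adjusted. Unless the pretest SD is about half the post-treatment SD or less, the contrast falls short of the power used to justify N = 90. Attrition would lower both figures: for an assumed 10% to 20% loss at k = 1, the plan's covariate method gives 76% to 70% and the change contrast 60% to 54%.

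The planned interaction is still a valid randomised comparison, so the cost is precision and not bias. For self-efficacy it is about 4 points at k = 1. This should be fixed.

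**What to change.** Keep the REML multilevel model with three time points, but constrain the three groups to one common pre-treatment mean: time and group-by-time terms, no group main effect, unstructured covariance. Write this parameterisation into Aim 1, and name the group contrasts at post-treatment and at follow-up as the tests. The constraint is justified by design, since the protocol's Assignment to Study Group section has all pre-treatment assessments collected before randomisation. Because Aim 3 reuses these models, state there how parenting stress enters at pre-treatment.

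An alternative is to model only post-treatment and follow-up, with pretest-by-time as covariate. It matches the power section equally well but costs more: pre-treatment leaves the time factor, so Aim 1 loses its pre-to-post time effect and the Aim 3 interactions with time change meaning.

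If the full-factorial model is kept, restate the fidelity power for it, with its alpha, SD ratio and contrast. Under equal SDs and alpha .05 that is about 65% for the post-treatment contrast.

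The preferred change costs SAP wording and a small edit to model syntax. It needs no new data.
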